6.2 Trial Procedures

The Trial Flow Chart - Section 6.0 summarizes the trial procedures to be performed at each visit. Individual trial procedures are described in detail below. It may be necessary to perform these procedures at unscheduled time points if deemed clinically necessary by the investigator.

Furthermore, additional evaluations/testing may be deemed necessary by the Sponsor and/or Merck for reasons related to subject safety. In some cases, such evaluation/testing may be potentially sensitive in nature (e.g., HIV, Hepatitis C, etc.), and thus local regulations may require that additional informed consent be obtained from the subject. In these cases, such evaluations/testing will be performed in accordance with those regulations.

6.2.1 Administrative Procedures

6.2.1.1 Informed Consent

The Investigator must obtain documented consent from each potential subject prior to participating in a clinical trial.

6.2.1.1.1 General Informed Consent

Consent must be documented by the subject's dated signature or by the subject's legally acceptable representative's dated signature on a consent form along with the dated signature of the person conducting the consent discussion.

A copy of the signed and dated consent form should be given to the subject before participation in the trial.

The initial informed consent form, any subsequent revised written informed consent form and any written information provided to the subject must receive the IRB/ERC's approval/favorable opinion in advance of use. The subject or his/her legally acceptable representative should be informed in a timely manner if new information becomes available that may be relevant to the subject's willingness to continue participation in the trial. The communication of this information will be provided and documented via a revised consent form or addendum to the original consent form that captures the subject's dated signature or by the subject's legally acceptable representative's dated signature.

Specifics about a trial and the trial population will be added to the consent form template at the protocol level.

Product: Pembrolizumab and Lenalidomide
Protocol/Amendment No.: Version 3.1 July 18th, 2017

The informed consent will adhere to IRB/ERC requirements, applicable laws and regulations and Sponsor requirements.

6.2.1.2 Inclusion/Exclusion Criteria

All inclusion and exclusion criteria will be reviewed by the investigator or qualified designee to ensure that the subject qualifies for the trial.

6.2.1.3 Medical History

A medical history will be obtained by the investigator or qualified designee. Medical history will include all active conditions, and any condition diagnosed within the prior 10 years that are considered to be clinically significant by the Investigator. Details regarding the disease for which the subject has enrolled in this study will be recorded separately and not listed as medical history.

6.2.1.4 Prior and Concomitant Medications Review

6.2.1.4.1 Prior Medications

The investigator or qualified designee will review prior medication use, including any protocol-specified washout requirement, and record prior medication taken by the subject within 28 days before starting the trial. Treatment for the disease for which the subject has enrolled in this study will be recorded separately and not listed as a prior medication.

6.2.1.4.2 Concomitant Medications

The investigator or qualified designee will record medication, if any, taken by the subject during the trial. All medications related to reportable SAEs and ECIs should be recorded as defined in Section 7.2.

6.2.1.5 Disease Details and Treatments

6.2.1.5.1 Disease Details

The investigator or qualified designee will obtain prior and current details regarding disease status.

6.2.1.5.2 Prior Treatment Details

The investigator or qualified designee will review all prior cancer treatments including systemic treatments, radiation and surgeries.

Product: Pembrolizumab and Lenalidomide
Protocol/Amendment No.: Version 3.1 July 18th, 2017

6.2.1.5.3 Subsequent Anti-Cancer Therapy Status

The investigator or qualified designee will review all new anti-neoplastic therapy initiated after the last dose of trial treatment. If a subject initiates a new anti-cancer therapy within 30 days after the last dose of trial treatment, the 30 day Safety Follow-up visit must occur before the first dose of the new therapy. Once new anti-cancer therapy has been initiated the subject will move into survival follow-up.

6.2.1.6 Assignment of Screening Number

6.2.1.7 Trial Compliance (Medication/Diet/Activity/Other)

Pembrolizumab will be administered as an infusion. Compliance check to lenalidomide tablets will be performed by the clinic staff at each visit, subjects will be asked to bring at each follow up the bottle of medication for tablet count check.

6.2.2 Clinical Procedures/Assessments

6.2.2.1 Adverse Event (AE) Monitoring

The investigator or qualified designee will assess each subject to evaluate for potential new or worsening AEs as specified in the Trial Flow Chart and more frequently if clinically indicated. Adverse experiences will be graded and recorded throughout the study and during the follow-up period according to NCI CTCAE Version 4.0 (see Section 11.2). Toxicities will be characterized in terms regarding seriousness, causality, toxicity grading, and action taken with regard to trial treatment.

For subjects receiving treatment with pembrolizumab all AEs of unknown etiology associated with pembrolizumab exposure should be evaluated to determine if it is possibly an event of clinical interest (ECI) of a potentially immunologic etiology (termed immune-related adverse events, or irAEs); see the separate ECI guidance document in Appendix 4 regarding the identification, evaluation and management of potential irAEs.

Please refer to section 7.2 for detailed information regarding the assessment and recording of AEs.

6.2.2.2 Full Physical Exam

The investigator or qualified designee will perform a complete physical exam during the screening period. Clinically significant abnormal findings should be recorded as medical history. A full physical exam should be performed during screening,

Product: Pembrolizumab and Lenalidomide
Protocol/Amendment No.: Version 3.1 July 18th, 2017

6.2.2.3 Directed Physical Exam

For cycles that do not require a full physical exam per the Trial Flow Chart, the investigator or qualified designee will perform a directed physical exam as clinically indicated prior to trial treatment administration.

6.2.2.4 Vital Signs

The investigator or qualified designee will take vital signs at screening, prior to the administration of each dose of trial treatment and at treatment discontinuation as specified in the Trial Flow Chart (Section 6.0). Vital signs should include temperature, pulse, respiratory rate, weight and blood pressure. Height will be measured at screening only.

6.2.2.5 Eastern Cooperative Oncology Group (ECOG) Performance Scale

The investigator or qualified designee will assess ECOG status (see Section 11.1) at screening, prior to the administration of each dose of trial treatment and discontinuation of trial treatment as specified in the Trial Flow Chart.

6.2.2.6 Tumor Imaging and Assessment of Disease

Assessment of lymphoma response (CR, PR or SD) and disease progression will be evaluated according to the Revised Response Criteria for Malignant Lymphoma²⁴. A full IV contrast CT scan combined with a PET scan is preferred for baseline evaluation, interim evaluation (q 12 weeks per standard of care), and at the completion of study. Overall response will be measured for all patients who complete one cycle of treatment. Kaplan-Meier methodology will be used to estimate median PFS and OS.

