5.2 Patient Recruitment and Registration

Patients will be recruited from the Investigators' clinical practices at the Perlmutter Cancer Center (PCC) at NYU Langone Health, Winship Cancer Institute of Emory University, Massachusetts General Hospital (MGH) and Beth Israel Deaconess Medical Center of MGH in Boston, MA. Prior to study entry, a patient's eligibility must be approved in writing by the NYU Clinical Trials Office.

Target accrual for this study is 26-29 patients. Prospective subjects will receive detailed information regarding this study; its investigational nature, required study procedures, alternative treatments, risks and potential benefits of the study. All questions will be answered by the PI and/or qualified research personnel.

The Principal Investigator will:

1. Obtain signed and dated informed consent from the potential subject before any study specific procedures are performed.

2. Determine patient eligibility. (See Section 5.1.2 and 5.1.3)
3. Submit registration to NYU Langone Health Perlmutter Cancer Center Clinical Trials Office (CTO)
4. Receive registration confirmation from the designated CTO staff member at NYU Perlmutter Cancer Center CTO, including a unique study identification number assigned to the patient, which will be distributed to the study team upon registration of the patient.

Enrollment in the study requires that all inclusion and exclusion criteria have been met. Enrollment occurs upon confirmation of registration from the NYU Langone Health Perlmutter Cancer Center (PCC) Clinical Trials Office (CTO). The following materials must be submitted to the research coordinator for registration:

1. Complete signed and dated informed consent form
2. Complete signed and dated eligibility checklist
3. All supporting documentation verifying each criterion has been met

Registration will occur within 48 hours of research coordinator receipt of all of the above documents. A written confirmation of enrollment including a unique study identification number assigned by the research coordinator will be disbursed to the study team upon registration. The patient will not be identified by name. This is the point, at which, the patient is considered accrued on study.

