5.8 Subject Replacement Strategy

If a subject drops out of the study before the first evaluation for reasons different than disease progression or death related to underlying lymphoma or toxicity from the treatment, he or she might be replaced.

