		^a Every week +/- 3 days; except Cycle 1 ^b Day 1 of 21 day cycle ^c Day 1-14 of 21 day cycle ^Λ Every 12 weeks +/- 1 week ^β Biopsy while on therapy is optional ^c For women of child bearing potential: Pregnancy test is required 10-14 days prior to first dose of study drug AND a second pregnancy test is required within 24 hours before first dose of study drug														

Product: Pembrolizumab and Lenalidomide
Protocol/Amendment No.: Version 3.1 July 18th, 2017

TRIAL PROCEDURES

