6.2.3.2 Withdrawal/Discontinuation

When a subject discontinues/withdraws prior to trial completion, all applicable activities scheduled for the final trial visit should be performed at the time of discontinuation. Any adverse events which are present at the time of discontinuation/withdrawal should be followed in accordance with the safety requirements outlined in Section 7.2 - Assessing and Recording Adverse Events. Subjects who a) attain a CR or b) complete 24 months of treatment with pembrolizumab may discontinue treatment with the option of restarting treatment if they meet the criteria specified in Section 7.1.5.5. After discontinuing treatment following assessment of CR, these subjects should return to the site for a Safety Follow-up Visit (described in Section 7.1.5.3.1) and then proceed to the Follow-Up Period of the study (described in Section 7.1.5.4).

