6.2.4.4 Follow-up Visits

Subjects who discontinue trial treatment for a reason other than disease progression will move into the Follow-Up Phase and tumor imaging will occur every 12 weeks (\pm 7 days). Every effort should be made to collect information regarding disease status until the start of new anti-neoplastic therapy, disease progression, death, end of the study or if the subject begins retreatment with pembrolizumab as detailed in Section 7.1.5.5. Information regarding post-study anti-neoplastic treatment will be collected if new treatment is initiated.

Product: Pembrolizumab and Lenalidomide
Protocol/Amendment No.: Version 3.1 July 18th, 2017

Subjects who are eligible to receive retreatment with pembrolizumab according to the criteria in Section 7.1.5.5 will move from the follow-up phase to the Second Course Phase when they experience disease progression.

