7.2 Phase II Statistical Analysis Plan

This is an open label single arm Phase II study to test the hypothesis that the CR rate is less than or equal to 20% versus the alternative hypothesis that the CR rate is greater than or equal to 50%.

Our sample size estimate is based on our primary hypothesis that evaluates CR rate in the HL cohort. One-sided binomial tests will be used to assess these changes. Given a baseline CR of 21% for single agent pembrolizumab in relapsed HL, we hypothesize that combination of lenalidomide and pembrolizumab will have a CR rate of 50% or greater for the combination at a significance level of 0.05 with 80% power (PASS, 2008).

With 17 patients entered into this trial, with 83% power and alpha of 0.04, we can reject the null hypothesis if 6 or fewer responses are observed.

Patient and disease characteristics will be summarized at baseline using descriptive statistics (means, medians, quartiles, standard deviations, etc.) and graphical displays including boxplots for continuous variables and frequency distributions for qualitative variables.

The complete response rate will be estimated with exact 95% confidence intervals. Other secondary response measures will be summarized using frequency distributions. Distributions of dose and time on treatment will also be summarized. Time to failure will be estimated using Kaplan Meier methods (failures include progression or death, death). Descriptive summaries of response duration and transfusion independence duration will also be summarized using Kaplan Meier methods ²⁵.

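### Section 7.2 names no analysis set for the CR rate, and the only population statement for response points to cycle-1 completers rather than the 17 patients the design counts

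*Combined protocol and SAP*

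**What the plan says.** Section 7.2 sets a one-sided binomial test of a CR rate of 20% or less against 50% or more. Its operating characteristics open with "With 17 patients entered into this trial", and for estimation it says "The complete response rate will be estimated with exact 95% confidence intervals". It does not say which patients form the denominator, or how a patient with no response assessment is counted. No other section defines an analysis set.

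Four other places bear on the question:

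- 6.2.2.6: "Overall response will be measured for all patients who complete one cycle of treatment". A cycle is 21 days (6.2.4.2).
- 5.2 fixes accrual at confirmation of registration: "This is the point, at which, the patient is considered accrued on study". So an entered patient could be one who was registered but never dosed.
- 5.8 allows replacement before the first evaluation only when the patient drops out "for reasons different than disease progression or death related to underlying lymphoma or toxicity from the treatment, he or she might be replaced".
- The Trial Flow Chart footnote puts tumor imaging at "Every 12 weeks +/- 1 week". Off-treatment scans are also foreseen. The flow chart has imaging at discontinuation. 6.2.3.2 says "all applicable activities scheduled for the final trial visit should be performed at the time of discontinuation". 6.2.4.4 says a subject who stops "for a reason other than disease progression will move into the Follow-Up Phase and tumor imaging will occur every 12 weeks". The plan does not say whether these scans count toward the primary CR rate.

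**The concern.** An analyst looking for a denominator will find one population statement tied to response, and it refers to patients who finish cycle 1. Used that way, it removes patients who progress, die or stop for toxicity in the first 21 days. Most of them are probably non-CRs, because the first on-treatment scan comes at about 12 weeks. Section 5.8 does not provide for replacing them, which suggests they were meant to stay in the count. The two sections are not reconciled.

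At stake are the reported CR rate, its interval and possibly the test, in an open-label single-arm comparison with a fixed 20% on 17 patients. The denominator should be settled before results are known.

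**Working it through.** **Inputs.** From 7.2: n = 17, null rate 0.20, alternative 0.50, one-sided exact binomial test at 0.05. From 4.1.3 (the single-agent pembrolizumab trial in relapsed HL): 29 patients reported, 7 stopped for progression and 1 for toxicity, median follow-up 153 days. Assumed, because the documents give no figure: cycle-1 loss d of 5, 10, 15 or 20%, and a CR rate among leavers q of 0 or 10%.

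**Step 1: the plan's own figures.** P(X ≥ 7 | 17, 0.20) = 0.0377 and P(X ≥ 7 | 17, 0.50) = 0.834. These match the stated 0.04 and 83%, with all 17 counted. (7.2 prints the rejection rule as 6 or fewer responses; that direction is a separate point. P(X ≤ 6 | 17, 0.20) is 0.962.)

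**Step 2: a rough anchor for early loss.** With a constant hazard, -ln(1 - 8/29)/153 = 0.00211 per day. Over 21 days the loss is 1 - exp(-21 × 0.00211) = 4.3%. This is crude: follow-up ranged from 1 to 341 days, and the combination may be more toxic than the single agent.

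**Step 3: effect on the estimate and on a re-run test.** Completers m follow Bin(17, 1 - d). If the CR rate among all entered patients is 0.20, the rate among completers is (0.20 - d·q)/(1 - d). The cut-off is re-derived for each m at one-sided 0.05 against 20% (7 for m = 15 to 17, 6 for m = 11 to 14, 5 for m = 10).

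| Loss d | Apparent rate, q = 0 | Type I, re-run, q = 0 | Chance of 3+ leavers | Apparent rate, q = 10% | Type I, re-run, q = 10% |
|---|---|---|---|---|---|
| 5% | 21.1% | 0.0395 | 0.05 | 20.5% | 0.0349 |
| 10% | 22.2% | 0.0479 | 0.24 | 21.1% | 0.0375 |
| 15% | 23.5% | 0.0612 | 0.48 | 21.8% | 0.0429 |
| 20% | 25.0% | 0.0767 | 0.69 | 22.5% | 0.0483 |

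Type I error passes 0.05 at d = 10.9% when q = 0, and at about 22% when q = 10%. At the 4.3% anchor with q = 0, it is about 0.039 and the chance of three or more leavers is about 0.03.

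**Step 4: when a result would change.** With 6 CRs, all among completers:

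- 6/17 = 35% (95% CI 14 to 62%), p = 0.106
- 6/16: p = 0.082
- 6/15: p = 0.061
- 6/14 = 43% (18 to 71%), p = 0.044

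Three of the 17 must be dropped before 6 CRs becomes significant.

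**Step 5: cut-off kept at 7 CRs.** The number of CRs counted follows Bin(17, 0.20 - d·q) under the null. If q = 0, the test is the same as on all 17: 0.0377 and 0.834. If q = 10%, type I error is 0.033, 0.029, 0.025 and 0.022 at 5, 10, 15 and 20% loss. Power, using 0.50 - d·q, falls from 0.823 at 5% to 0.789 at 20%.

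**The case against.** The sentence in 6.2.2.6 sits in a procedures section. It says who has overall response measured; it does not say only these patients, and it does not call them evaluable or the denominator. It also speaks of overall response rather than the CR test, and 3.1 makes ORR the Phase 2 primary objective. The power statement and the replacement rule both lean toward counting everyone. All of that stands: the completer denominator is a possible reading, not a stated rule. The missing definition applies equally to ORR.

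The size of the problem is also open to challenge. The background figures point to about 4% loss in 21 days, and entry requires ECOG 0 to 1. The 15% and 20% rows have no support in the documents and serve only as stress tests. Even at 10% loss, with every leaver a non-CR, type I error stays below 0.05.

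A reader might infer that the plan excludes early failures and so inflates the primary test. The documents do not support that: the exclusion is not stated, and inflation above 0.05 needs both a re-derived cut-off and fairly high early loss. A reader might also infer that a fixed cut-off of 7 makes the denominator irrelevant to the test. That is true only if every leaver is a non-CR. Because scans at discontinuation and in follow-up could show a CR in a leaver, exclusion could instead make the test conservative and cost power.

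**Conclusion.** The gap is real and should be closed. The plan does not say who is in the CR rate, its interval or its test; its one population statement for response conflicts with the 17-patient basis that reproduces its alpha and power.

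The likely consequence is small: at 5% early loss with no CRs among leavers, about one percentage point on a true 20% rate and a re-run type I error of 0.040 against 0.038. The upward shift assumes that leavers have a lower CR rate than completers; there is no shift if nobody leaves in cycle 1. All loss rates are assumptions, and the 4% anchor depends on a constant hazard and single-agent data. This is a bias to prevent by wording, not evidence that the design fails.

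**What to change.** In 7.2, state that:

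- the CR rate, exact interval and test use all Phase 2 HL patients who receive at least one dose;
- any post-baseline assessment before new anti-cancer therapy counts, including scans at discontinuation or in follow-up;
- dosed patients with no post-baseline assessment count as non-CR.

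In 6.2.2.6, label the cycle-1-completer analysis as a sensitivity analysis.

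Also state the rejection cut-off if the analysed number is not 17. Against 20% at one-sided 0.05 it is 7 CRs for n = 16 (power at 50%: 0.773) and 8 CRs for n = 18 to 20 (0.760, 0.820 and 0.868).

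Finally, state how dosed patients replaced under 5.8 are handled. This is a trade-off for the sponsor to settle. Keeping one such patient gives n = 18 and a cut-off of 8, with power 0.760 (0.685 if that patient is a certain non-CR); keeping the cut-off at 7 would give type I error 0.051. Leaving the patient out preserves 17 but assumes that the reason for dropping out is unrelated to response.

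The cost is a few sentences and a reported CR rate that may be slightly lower.

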6.2.2.7 Tumor Tissue Collection and Correlative Studies Blood Sampling

- a) Samples of peripheral blood will be collected pretreatment, at initial staging and at the end of the study in all patients. On these samples flow cytometry, and other immune analysis will be performed to characterize the peripheral blood mononuclear cells populations and their variation as a function of the therapy, and to evaluate circulating immune subsets in patients as a function of treatment.
- b) Immunohistochemistry evaluation of the tumor microenvironment will be performed on patient's initial biopsy. Optional core needle biopsy early during therapy and in relapsing patients at the time of relapse will be submitted for analysis and comparison
- c) Gene expression profiling of the above samples will be concurrently analyzed in collaboration with [name] at BCC Cancer Center.

Product: Pembrolizumab and Lenalidomide
Protocol/Amendment No.: Version 3.1 July 18th, 2017

- d) Evaluation of PD-1 expression in tumor tissue will be performed in collaboration with Merck.

Tissue and blood storage

All blood and tissue samples will be processed immediately and stored indefinitely for later analysis in a locked -80°C freezer in the NYU Biorepository Core for research purposes only. No germline genetic testing will be performed on any specimens collected during this trial. Subjects will not receive the results of any testing.

These specimens will not be linked to any clinical data and will be de-identified in the clinical research database. Only the PI and data manager will have the linking key. Only the investigators listed on this protocol will have access to these samples. After both blood and tissue samples are analyzed at a later date unutilized samples will be preserved indefinitely in the NYU Biorepository for potential future research. All patients enrolled will be given a unique identifier. Only the data manager will know the code linking patient and study ID number. Patients will be assigned a unique code number. All specimens collected will be deidentified and assigned the same unique study number of the corresponding patient and will also be marked with the collection time point. Clinical information regarding toxicities and response will likewise be stored in a deidentified database using only the unique identifier. For patients enrolled at a participating site, measures to assure secure and HIPAA compliant storage of quality biospecimens will be determined by participating site institutional protocols. Storage of tissue and blood for future research is optional. Patients may decide to withdraw their samples from storage or future use at any time after informed consent either verbally or in writing.

